4.3.2 Acoustic Angiography Imaging Procedures

Acoustic angiography imaging involves a research ultrasound scanner (Verasonics Vantage 256; see section 5.0) as well as conventional b-mode ultrasound to guide the location of the imaging. The conventional ultrasound will be conducted just prior to the acoustic angiography for localization. Imaging will be performed within the package insert guidelines for ultrasound system mechanical index (a measurement of output power) when imaging perflutren contrast agent (less than 0.8).

Acoustic angiography imaging will be performed by a trained medical personnel using mild compression to eliminate motion. Total imaging time is estimated to be less than 15 minutes. All image data will be de-identified and transferred for off-line analysis based on a study ID. The research images will NOT be interpreted or analyzed for clinical decisions related to the patient. See section 5.0 for additional information on the acoustic angiography device.

4.4 Standard of Care Biopsy

The patient will then undergo her scheduled breast biopsy procedure based on the pre-study diagnostic imaging. The research acoustic angiography imaging will NOT be interpreted prior to the breast biopsy and therefore will not influence any clinical decision concerning the biopsy.

4.5 Medical Record Abstraction

The primary objective of this study is to determine the sensitivity and specificity of acoustic angiography imaging. In order to meet this objective, we will review each patient's clinical records, including their pathology

report from biopsy. The malignancy will be determined as indicated by the pathology report.

4.6 Reader Study

A total of five readers (radiologists trained in breast imaging) will be recruited to participate in evaluation of all imaging performed under LCCC1748.

In the reader preference study, each reader will be asked to compare the acoustic angiography case to the conventional b-mode ultrasound case to evaluate the imaging characteristics based on the BIRADS ultrasound lexicon

(<http://www.acr.org/~media/ACR/Documents/PDF/QualitySafety/Resources/BIRADS/USLexiconClass.pdf>). Specifically the relative ability to evaluate shape, margins and vascularity will be evaluated using a seven-point scale (-3 to +3) for the paired modality comparisons for each of the 60 cases. The order that the modalities will be presented to the radiologists are randomized. The first modality presented for the specimen will be considered the primary and the second modality presented will be considered the secondary for the survey instrument. After a washout period of four weeks, the modalities will be presented in reverse.

The data collection form for the reader study portion is given in Appendix A, section 13.1.

The readers will be asked to assign a subjective malignancy score (-2 (highly not malignant) to +2 (highly malignant)) and their confidence for each lesion for each modality (0 to 100%). These will also be documented on the form in Appendix A. These scores will be used combined for a binary analysis. Malignancy scores of +1 and +2 will be considered malignant. Scores of -2, -1, and 0 will be considered not malignant. The confidence of malignancy will be used independently in the analysis.

5.0 Research Ultrasound Scanner: Verasonics Vantage 256

The device used for this study will be a programmable research ultrasound scanner (Vantage 256, Verasonics, Inc., Kirkland, WA, USA) and a unique probe developed in conjunction with the research lab run by [name] (Sunnybrook Research Institute, Toronto, ON, Canada) and VisualSonics (FUJIFILM VisualSonics, Inc., Toronto, ON, Canada). The ultrasound probe developed is a modification of a preclinical high frequency transducer, modified to house a dual-frequency linear array.

The Vantage 256 is a programmable research ultrasound system. It is marketed commercially by Verasonics, Inc. For this study, two Vantage 256 platforms will be used. Each system will be programmed for

diagnostic ultrasound imaging at acoustic exposures similar to those approved for clinical use. This ultrasound system and similar models have been designated to pose no significant risk in other clinical trials by the respective IRBs or other similar regulatory agencies responsible for compliance oversight of these studies when acoustic output is maintained at or below FDA-approved levels (see section 13.1, Appendix B).

Verasonics Vantage
Research Ultrasound System

Figure 1. Device Image

Dual-Frequency Transducers:

The probes we plan to use in this study are modified VisualSonics probes. They are dual-frequency linear transducer arrays. We plan to run the transducers in 2 modes during the study: b-mode and dual-frequency contrast mode. In b-mode, only the high frequency elements are transmitting and receiving ultrasound. B-mode imaging will be performed using a designated b-mode program on one Vantage 256 scanner. In dual-frequency contrast mode, the low frequency elements transmit ultrasound and the high frequency elements receive the signal. To do so, one Vantage 256 controls the low frequency elements, and a second Vantage 256 controls the high frequency elements. Operation of the systems is synchronized and controlled by one designated dual-frequency program. It should be noted that only *one* Vantage system will be transmitting at any given time. The center frequency is 2 MHz for the low frequency elements and 20 MHz for the high frequency elements.

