10.1 Sample Size and Accrual

10.1.1 Primary analysis

For power calculation, the null hypothesis is that the specificity of acoustic angiography system is the same as the standard of care (b-mode ultrasound), which is assumed to be 70%. (We will determine the specificity of b-mode ultrasound during the trial to confirm that the 70%

represents the specificity in the hands of UNC radiologists) Under the alternative, we expect that the specificity of the new device is at least 90%. The specificities are measured relative to pathological diagnosis as the reference standard. With 60 lesions and 5 readers, where we anticipate that roughly half will be malignant, assuming the correlation from the same patient to be 0.5 and the readers to read different patients independently, the power to see specificity at least larger than 90% is 88% (the variance of the estimated specificity is calculated to be less than $0.6^2 \cdot 0.25/30$) at the significance level 0.05 using one-side test. Although we will study both sensitivity and specificity, our power calculation is based on specificity.

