10.2 Data Analysis Plans

10.2.1 Primary Analysis

This is a prospective study to assess the diagnostic performance of the newly developed device. The **primary outcome of interest is the sensitivity and specificity of the acoustic angiography device as compared to b-mode ultrasound**. The sensitivity and specificity can be estimated non-parametrically as the proportion of the lesions which are distinguished as malignant versus non-malignant compared to the reference. This estimate will be calculated for each reader then averaged over all the readers. The standard error of the average sensitivity and specificity estimate will be calculated using the bootstrap method, where each patient is treated as independent unit with 5 ratings. The confidence interval of the final estimate will be provided using the normality assumption.

Furthermore, we will estimate the sensitivity and specificity of the b-mode ultrasound in this study and compare it with the sensitivity and specificity estimate of the acoustic angiography device using the bootstrap approach and the confidence interval of their differences will be provided using the normality assumption.

Malignancy scores of +1 and +2 will be considered malignant. Scores of -2, -1, and 0 will be considered not malignant. The confidence of malignancy will be used independently

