13.0 APPENDICES

13.1 Appendix A: Reader Study Data Collection Form

Specimen: _____

Reader: _____

Date: _____

Overall Assessment:

Primary

Overall specimen malignancy score (-2 to +2): _____

Malignancy confidence (0-100) _____ %

Secondary

Overall specimen malignancy score (-2 to +2): _____

Malignancy confidence (0-100) _____ %

1. Primary versus Secondary Shape/Morphology

+3	I am significantly more confident in the Primary representation of the lesion shape/morphology I described as compared to Secondary representation of the same lesion
+2	I am more confident in the Primary representation of the lesion shape/morphology I described as compared to Secondary representation of the same lesion
+1	I am slightly more confident in the Primary representation of the lesion shape/morphology I described as compared to the Secondary representation of the same lesion.
0	I have the same confidence in the Primary representation of the lesion shape/morphology I described as I do in the Secondary representation of the same lesion
-1	I am slightly less confident in the Primary representation of the lesion shape/morphology I described as compared to the Secondary representation of the same lesion.
-2	I am less confident in the Primary representation of the lesion shape/morphology I described as compared to the Secondary representation of the same lesion.
-3	I am significantly less confident in the Primary representation of the lesion shape/morphology I described as compared to the Secondary representation of the same lesion.

2. Primary versus Secondary: Vascularity

+3	I am significantly more confident in the Primary representation of the lesion vascularity I described as compared to the Secondary representation of the same lesion.
+2	I am more confident in the Primary representation of the lesion vascularity I described as compared to Secondary representation of the same lesion
+1	I am slightly more confident in the Primary representation of the lesion vascularity I described as compared to the Secondary representation of the same lesion.
0	I have the same confidence in the Primary representation of the lesion vascularity I described as I do in the Secondary representation of the same lesion.
-1	I am slightly less confident in the Primary representation of the lesion vascularity I described as compared to the Secondary representation of the same lesion.

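### Second-look malignancy scores, given after the reader has seen the other modality of the same lesion, can enter the primary sensitivity and specificity

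*Combined protocol and SAP*

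**What the plan says.** Section 4.6 (Reader Study) has five radiologists evaluate all 60 cases. Its paragraph on reader preference sets the presentation scheme. Order is left to chance: "The order that the modalities will be presented to the radiologists are randomized". Position, not modality, then decides which image counts as Primary on the form: "The first modality presented for the specimen will be considered the primary and the second modality presented will be considered the secondary". A second session swaps the order: "After a washout period of four weeks, the modalities will be presented in reverse".

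A later paragraph of 4.6 asks each reader for a malignancy score and a confidence for each lesion under each modality, and adds: "These will also be documented on the form in Appendix A". That form (Section 13.1, Appendix A) has one specimen field, one reader field and one date field. It asks for a malignancy score (the line begins "Overall specimen malignancy score (-2 to +2") and a confidence for the Primary image, then the same for the Secondary image, and then the head-to-head preference items.

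Section 10.2.1 computes sensitivity and specificity per reader from the dichotomized malignancy score, averages over readers, and bootstraps patients, "where each patient is treated as independent unit with 5 ratings". It does not say which session or which presentation position supplies those ratings. For the sample size, Section 10.1.1 states that "the power to see specificity at least larger than 90% is 88" percent, one-sided at 0.05, against a specificity fixed at 70%.

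**The concern.** The primary objective is to compare the accuracy of two modalities, so each estimate should rest on what a reader concludes from that modality. When a reader scores the second-presented image of a lesion, the other image has just been seen and scored. If the first score is not fixed by then, it too could be changed in the light of the second image.

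The existing safeguards address something else. Randomizing and reversing the order spreads second looks evenly over the two modalities, but the second looks remain in the data. The washout separates the two presentation orders; within a session the two modalities of a lesion are scored on the same dated form.

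At stake is what the primary estimates mean, and possibly the size of the difference between modalities. If malignancy is scored in both sessions, there are also more scores than Section 10.2.1 uses, with no rule for choosing among them.

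**Working it through.** **Which scores exist.** Each session gives 5 readers × 60 cases = 300 forms, each with two malignancy scores: 600 scores, of which 300 are first looks and 300 second looks.

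- *One scored session:* 600 / (60 lesions × 2 modalities) = 5 scores per lesion and modality. If order is randomized evenly, about half are expected to be second looks.
- *Two scored sessions:* 1,200 / 120 = 10 scores per lesion and modality. With order reversed for each reader and lesion, 5 are first looks and 5 are second looks.

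Five ratings therefore fits either all scores from one session or the first looks from two. Section 10.2.1 does not say which.

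**The plan's power figure.** Inputs from 10.1.1: 30 benign lesions (half of 60), 5 readers, within-patient correlation 0.5, specificity 90% against a fixed 70%, one-sided 0.05, and p(1−p) bounded by 0.25.

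- Design factor: (1 + 4 × 0.5)/5 = 0.6
- Variance: 0.6 × 0.25/30 = 0.005, so SE = 0.0707
- Power: Φ(0.20/0.0707 − 1.645) = 0.882, matching 88%

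The variance as printed squares the 0.6. That gives SE 0.0548 and 97.8%, so the unsquared form is used here. The printed square is a separate matter.

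**Illustration 1: some second-look calls repeat the first call.** Let w be the share of second-look calls overwritten by the first call, with half of the reads being second looks. Both are assumptions; the documents give no value.

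- Acoustic angiography observed: 0.90 − 0.5 × w × 0.20 = 0.90 − 0.1w
- B-mode observed: 0.70 + 0.1w
- Within-study difference: 0.20 × (1 − w)

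| w | Acoustic angiography | Gap from fixed 70% | Power, variance bound | Power, binomial variance | Within-study difference |
|---|---|---|---|---|---|
| 0 | 90% | 20 | 88.2% | 98.6% | 20 |
| 0.1 | 89% | 19 | 85.1% | 97.0% | 18 |
| 0.2 | 88% | 18 | 81.6% | 94.5% | 16 |
| 0.3 | 87% | 17 | 77.6% | 90.9% | 14 |

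The binomial column uses null SE √(0.6 × 0.21/30) = 0.0648 and alternative SE √(0.6 × p(1−p)/30). Both power columns refer to the gap from the fixed 70%, where only the fall in acoustic angiography counts. They are not powers for the within-study difference in the last column. That power needs the correlation between the two modalities' calls, which the documents do not give.

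If second looks are 40% or 60% of reads, power at w = 0.3 on the variance bound is 80.1% or 75.0%.

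**Illustration 2: the effect can be zero or reversed.** If both modalities gain equally on second look, the difference between them is unchanged. If both truly have 70% specificity and only second-look acoustic angiography gains 5 or 10 points, the observed gain is 2.5 or 5 points. The one-sided error is then Φ(0.025/0.0707 − 1.645) = 9.8% or Φ(0.05/0.0707 − 1.645) = 17.4%.

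**Using all ten reads.** The factor is (1 + 9 × 0.5)/10 = 0.55, giving power 90.5% against 88.2%, if the 0.5 correlation holds across all ten. The choice of reads is thus mainly about bias and selection, not precision.

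**First looks from session 1 only.**

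- Order balanced across readers within each lesion (2 or 3 first looks): mean factor (0.750 + 0.667)/2 = 0.708, SE 0.0768, power 83.1%.
- One order per lesion for all readers (15 benign lesions with 5 reads): SE √(0.6 × 0.25/15) = 0.100, power 63.9%.

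**The case against.** The strongest reply has five parts.

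- *The missing lock is an argument from silence.* Section 4.6 describes sequential presentation, and the form lists the Primary score before the Secondary, so a reader would naturally score in that order. One date shows same-day reading, not side-by-side display or back-editing. This stands: the documents do not show that readers will revise first scores. But sequential scoring does not stop the first image from informing the second score, and no passage keeps second scores out of the analysis.
- *The two-session scheme belongs to the preference study.* It sits in that paragraph, and both 10.1.1 and 10.2.1 fit one score per reader, lesion and modality. A reader might infer that ten ratings are certain. The text does not state that; only the shared form, which carries malignancy fields in the reversed session too, suggests it. With one session, however, about half of the five are expected to be second looks, so the core point remains.
- *The pooling sentence.* From "These scores will be used combined for a binary analysis" a reader might infer that sessions, or score and confidence, are to be merged in some unspecified way. The sentences that follow do not support this: they collapse five score categories to two and keep confidence separate.
- *Size and direction are unknown.* A reader might infer bias in favour of acoustic angiography, or a definite loss of power. Neither is supported. Carry-over can shrink the difference, leave it alone or inflate it.
- *Acoustic angiography is acquired with b-mode guidance, so a read informed by b-mode may be the intended use.* Sections 1.3.1 and 4.3.2 describe b-mode as locating the lesion during imaging. Section 4.6 asks for a separate score for each modality, and the objective compares the two. If a combined read is intended, the plan should say so.

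**Conclusion.** The point holds as a gap in how the primary data are collected and selected. As written, the plan lets scores that may reflect both images enter estimates meant to describe one modality, and randomized, reversed order does not prevent that. No stated figure in the plan is wrong because of it.

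How much it matters cannot be known from the documents. In the overwriting illustration, power against the fixed 70% falls by about 3 to 11 percentage points on the plan's variance bound (88.2% to 85.1% or 77.6%), and by less with binomial variances. Separately, the within-study difference shrinks by 2 to 6 points. These figures rest on assumed overwriting of 10% to 30% and on half of the reads being second looks. The case for change rests on a clean definition of the estimate and a pre-stated choice of reads, not on a particular loss of power. It is a cheap improvement worth making before reading starts.

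**What to change.** **Section 4.6.** State that the randomized order, washout and reversal apply to the malignancy scores, and state the unit of order randomization. Require the Primary score and confidence to be recorded and locked before the Secondary image is shown.

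**Section 10.2.1.** Define the primary-analysis score as the one given to the first-presented modality in each session. Because order is reversed, this gives one read per reader, lesion and modality, that is, the planned five ratings, and the 88% calculation against a fixed 70% is unchanged.

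**Section 10.2.2.** Use the confidence from the same reads for the AUC.

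**Supportive analyses.** Report all reads, and session-1 first looks only. The precision of the latter depends on the unit of order randomization, as shown above.

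**Cost.** Wording changes and one reader instruction. If only one scored session was intended, the malignancy fields must also be completed on the 300 session-2 forms already planned for the preference study.

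**Downsides.**

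- Second-look scores leave the primary analysis.
- First looks in session 2 still rely on the four-week washout, because the reader saw both images in session 1.
- Each reader's two modality reads of a lesion come from different sessions. This may lower their correlation and slightly widen the interval for the paired difference.

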5.1 Expected Risks

5.1.1 Verasonics Vantage 256

This research protocol presents minimal risk to participants, investigators and study personnel. Our preliminary experimental and theoretical data show that the proposed stack design does effectively preserve excellent independent transmission of the two beams from the same aperture. Additional FEM modeling will be conducted to look at minimizing HF pulse distortion by varying the interlayer thicknesses and acoustic properties. The LF device will be designed to produce pulses with a mechanical index below the FDA limit of 1.9. Materials and processes will be adjusted to ensure that the probe temperature does not increase more than 6°C, as stated by the FDA.⁵² Thermal effects will also be modeled using finite element methods (PZFlex). Analysis of the low frequency beam will be performed to optimize the number and lateral extent of low frequency elements. The current transducer design contains 32 LF elements, which we believe should be enough in the low frequency array. Based on simulations and experimental findings, however, future transducer iterations may extend this to 64 elements for improved imaging performance. Although the high frequency array by itself has been previously optimized with respect to its use in preclinical VisualSonics systems, the dual-frequency variant and effects of the various polymer and metal layers within flex circuits required for element connectivity will need to be included within the acoustic modeling of the transducer stack.

5.2 Perflutren lipid (Definity)

See sections 1.4 and 6.1.5.

5.3 Duration of Study

It is anticipated that the total clinical study duration encompassing recruitment, enrollment, and data analysis will take approximately 2 years and will begin in year 4 of the grant. Active patient participation will last approximately 1 visit (consent and 15 minutes imaging).

6.0 Drug Information

6.1 Perflutren Lipid Microspheres (Lantheus Medical Imaging)

The Definity® vial contains components that upon activation yield perflutren lipid microspheres composed of octafluoropropane. Perflutren is a diagnostic drug that is intended to be used for contrast enhancement. The vial contains a clear, colorless, sterile, non-pyrogenic, hypertonic solution which is activated by mechanical agitation with Vialmix®.

Vialmix® is the activation device for use in the preparation of US contrast imaging agents, including Definity®. Prior to activation, each Definity® vial contains 6.52 mg/mL octafluoropropane in the headspace and 0.75 mg lipid blend (0.045 mg DPPA, 0.401 mg DPPC, and 0.304 mg MPEG5000

DPPE), 103.5 mg propylene glycol, 126.2 mg glycerin, 2.34 mg sodium phosphate monobasic monohydrate, 2.16 mg sodium phosphate dibasic heptahydrate and 4.87 mg sodium chloride in water in the clear liquid.

Upon activation, each mL of the milky white suspension contains a maximum of 1.2×10^{10} perflutren lipid microspheres with approximately 150 $\mu\text{L}/\text{mL}$ octafluoropropane.

6.1.1 Supplier/How Supplied

Perflutren (Definity®) will be provided to study subjects at no cost.

Perflutren is supplied as a single use 2mL clear glass vial containing clear liquid. Each package contains 4 single-use vials.

6.1.2 Handling and Dispensing of Perflutren

Perflutren lipid must be dispensed only from official study sites by authorized personnel according to local regulations. Perflutren should be stored in a secure area according to local regulations. It is the responsibility of the Investigator to ensure that study drug is only dispensed to study patients.

